6.3.1 Subject Analysis Sets18

6.3.2	Secondary Variables and Analyses	19
6.3.3	Safety	19
6.3.4	Other Data Summaries	19
7.	ADDITIONAL INFORMATION	19
7.1	USE OF ADDITIONAL MEDICAL SERVICES.....	19
7.2	SOURCE DATA VERIFICATION (SDV).....	19
7.3	TRIAL MONITORING.....	19
7.4	USE OF TRIAL FINDINGS.....	20
8.	ETHICAL AND LEGAL ISSUES	20
8.1	GOOD CLINICAL PRACTICES (GCP).....	20
8.2	APPROVAL OF PROTOCOL.....	20
8.3	CONFIDENTIALITY.....	20
8.4	INSURANCE/FINANCIAL.....	20
8.5	SUBJECT CONSENT.....	20
9.	REFERENCES	22

List of Abbreviations

AE	Adverse Event
cm	Centimeter
CRA	Clinical Research Associate
CRF	Case Report Form
FDA	U.S. Food & Drug Administration
GCP	Good Clinical Practice
ICH	International Conference on Harmonization
IEC	Independent Ethics Committee
in	Inch
IRB	Institutional Review Board
ITT	Intention-to-Treat
ODiv2.1a	Oswestry Disability Index version 2.1a
QoL	Quality-of-Life
SAE	Serious Adverse Event
SRS-22	Scoliosis Research Society -22 Outcomes
UADE	Unexpected Adverse Device Effect
VAS	Visual Analog Scale back and leg pain

SUMMARY

Title:	A Prospective, Multicenter, Randomized, Controlled Clinical Investigation of MONTAGE in Adults with Spinal Deformity undergoing Pedicle Subtraction Osteotomy
Short Title:	MONTAGE in PSO for Adult Spinal deformity
Protocol Number:	Montage 001-2017
Phase:	Phase 4-postmarketing
Methodology:	Prospective, randomized, open, controlled study
Study Duration:	2 years from entry of last subject
Follow-up:	2 years
Study Centers:	Multicenter study with up to 4-6 centers
Objectives:	Primary: To assess the safety and effectiveness of MONTAGE in reducing post-operative blood loss Secondary: To assess the PSO stability
Number of Subjects:	50 subjects
Diagnosis and Main Inclusion Criteria:	
 1. Presence of spinal deformity requiring a PSO 2. Patients aged 18-80 and 3. Non-smokers (must have quit smoking 6 months prior to surgery) and current smokers
Study Product, Dose, Regimen:	After surgically creating the wedged PSO defect, prior to closure of the osteotomy, patients will be randomized 1:1 to receive either MONTAGE applied to the cut surfaces for the osteotomy site or no hemostatic material.
Duration of Administration:	1 application during surgery
Reference Therapy:	Standard of care – no bone hemostat.

End-points and Statistical Methodology:

Efficacy Endpoint:

The primary efficacy outcome variable for the study is the amount of post-operative bleeding compared between patients randomized 1:1 to MONTAGE or standard of care (no bone hemostat). Blood loss will be measured indirectly by formulae that provide an estimate through changes in hematocrit. A 2-sided “t” test will be used for the analysis.

Safety Endpoints:

Consistent with the standard of care, successful reconstruction of the osteotomy site requires observation of the residual angle of the osteotomy and any gap that may be present. In order to demonstrate that the use of Montage does not negatively impact the desired outcome, any residual gap will be measured in millimeters and compared between the groups. This will be done by including a CT scan performed at 1-year post surgery. A 2-sided “t” test will be used for the analysis.

NRS back pain and NRS leg pain, SRS-22 and Oswestry Disability Index (ODIv2.1a) will be compared between the two groups and also reported as secondary outcome scores. Descriptive statistics will be reported.

PROTOCOL APPROVAL

Date
.....
.....
Date
.....
[name], Ph.D
Consultant Medical Officer
ABYRX

INVESTIGATOR AGREEMENT

The signing of this protocol by the Investigator signifies that the contents have been laid down in full agreement and that the trial will be conducted according Good Clinical Practice and to the procedures described.

.....
Date
<Investigator>

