3. TRIAL SUBJECT POPULATION

3.1 NUMBER OF SUBJECTS

A multicenter study will be undertaken in the US, with up to 4-6 centers contributing 50 patients (maximum of 20 patients per center). A sample size of 25 randomly assigned patients per study group (50 subjects in total) was calculated to detect a clinically significant treatment effect of MONTAGE (90% power; alpha = 0.05, 2-sided; 10% lost-to-follow up). This calculation was performed with the assumption that subjects within the control group lose on average 1,500 mL (+/- 500mL) of blood postoperatively while subjects within the treatment group will lose 1,000 mL of blood postoperatively.

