4.1.2 SAFETY OBJECTIVES

Safety objectives will include:

- Evaluation of the repaired osteotomy by measuring displacement of the edges of the bone under compression. The angular measurement is the angle between the superior endplate of the vertebral body below the PSO and the inferior endplate of the vertebral body above the PSO. Consistent with the standard of care, successful reconstruction of the osteotomy site requires observation of the residual

angle of the osteotomy and any gap that may be present. In order to demonstrate that the use of Montage does not negatively impact the desired outcome, any residual gap will be measured in millimeters and compared between the groups. This will be done by including a CT scan performed at 1-year post surgery. A 2-sided “t” test will be used for the analysis.

- To demonstrate that Montage does not interfere with the repair, evaluation of the formation of new bone, as measured by CT scans at 1-year post surgery.
- Evaluation using the VAS back pain and leg pain, Oswestry Disability Index (ODIv2.1a) and SRS-22, which will be recorded during the study and reported as outcomes scores, and compared between the two groups.
- Antifibrinolytics use and type will be recorded during the study and compared between the two groups

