4.2.1 Screening and Pre-Treatment Regimen

4.2.1.1 Visit #1: Screening Evaluation and Enrollment (Week -2)

- Signed written Informed Consent Form will be obtained.
- Subjects will be enrolled according to the Inclusion and Exclusion criteria listed above.
- Subject demographics, medical history, and vital signs will be recorded.
- A blood sample will be drawn from the subject for analysis of hematological and biochemical parameters at a central laboratory consistent with the study institutions preoperative workup
- Subjects will undergo pre-operative imaging using CT and radiographs, which are based on standard of care.
- Patient’s co-morbidities will be scored using the Charlson Comorbidity index, the ASA score as well as ISSG severity scores.

- A list of pain medications with dosing will be recorded
- VAS back and leg pain, ODIv2.1a and SRS-22 scores will be collected as a baseline.

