6. STATISTICAL DESIGN

6.1 DESIGN

This is a parallel group, randomized, open, multicenter, prospective study in subjects with spinal deformities requiring a PSO procedure at a single level. Patients will be randomized 1:1 to receive either MONTAGE or no bone hemostat. Within each randomization study group, patients will be stratified according to their smoking status (non-smokers versus current smokers).

The primary objective of this study is the evaluation of post-operative blood loss in the week following surgery.

The secondary outcome will be the stability of the construct, as measured by the gap between the repaired osteotomy edges. In addition, observations will be made regarding whether the hardware repair has been maintained, and if the screws have loosened, and if the inserted rods are intact. Each repair complication will be categorized as belonging to one of the following groups: 1) hardware malplacement, 2) loosening or dislodgment, 3) nonunion or nonfusion with hardware fracture 4) nonunion or nonfusion without hardware fracture 5) peri-hardware fracture. These complications will be measured with imaging, including CT scans performed at 1-year. Fusion failure will be determined to be present if an area of perihardware lucency greater than 2 mm in thickness is present.

Malplacement of hardware will be considered present when an abnormal hardware position with hardware impingement on an important structure such as nerve or vessel is present.

Other secondary objectives will include:

- The formation of new bone at the osteotomy site, measured in mms at 1-year post surgery at the osteotomy site.
- VAS back and leg, Oswestry Disability Index (ODIv2.1a), and SRS-22 scores which will be recorded during the study and reported as outcomes scores, and compared between the two groups.
- Analysis of the MONTAGE/vertebral body interface, evaluating whether bony substitution has occurred at 1-year post-surgery. The presence or absence of bony resorption around the MONTAGE will also be reviewed.
- The use and type of antifibrinolytics will be compared between the two groups.

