6.3 ANALYSIS PLAN

The statistical analysis will be performed in conjunction with Abyrx. Analyses will be conducted on the Intention-to-Treat population (ITT), with additional Per Protocol analyses. All significance tests will be two-sided; p-values will be provided with $P(H_0) < 0.05$ indicating a significant difference.

All other analyses with respect to demographic and clinical parameters will be reported with descriptive statistics.

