6.3.2 Secondary Variables and Analyses

Several secondary analyses will be carried out; the results of any secondary analyses are exploratory.

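### No baseline-adjusted comparison is specified for the pain, ODI and SRS-22 scores, although their baseline values are collected

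*Combined protocol and SAP*

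**What the plan says.** **Collection.** At the screening visit (section 4.2.1.1), "VAS back and leg pain, ODIv2.1a and SRS-22 scores will be collected as a baseline". The same scores are collected at Weeks 2, 6, 12, 24, 52 and 104 (sections 4.2.3.2 to 4.2.3.7).

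**Analysis.** Four places describe it, all in much the same way:
- Summary, Safety Endpoints: "NRS back pain and NRS leg pain, SRS-22 and Oswestry Disability Index (ODIv2.1a) will be compared between the two groups", followed by "and also reported as secondary outcome scores. Descriptive statistics will be reported".
- Section 1.4 lists the scores among the secondary objectives, to be compared between the groups.
- Section 4.1.2, Safety Objectives: "which will be recorded during the study and reported as outcomes scores, and compared between the two groups".
- Section 6.1: "scores which will be recorded during the study and reported as outcomes scores, and compared between the two groups".

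Two general rules also apply. Section 6.3 says "All other analyses with respect to demographic and clinical parameters will be reported with descriptive statistics", and section 6.3.2 says that "the results of any secondary analyses are exploratory". A t test is named for blood loss and for the residual gap, but not for these scores. No section names a covariate, a change score, a model or a main time point for them.

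**Two mismatches bear on the baseline.** Appendix I shows a question mark for SRS-22 at Baseline/Screening, where VAS and ODI have an X. The Summary calls the pain scale NRS; sections 1.4, 4.1.2, 4.2.1.1, 4.2.3.2 to 4.2.3.7 and 6.1 call it VAS, and Appendix I lists VAS.

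**The concern.** The trial collects a pre-operative value of each score and then describes a comparison that does not use it. In a trial of 50 patients this has two costs. A chance difference between arms at baseline passes in part into the follow-up comparison, and stratifying on smoking status (sections 4.1, 6.1 and 6.2) does not balance the scores. The estimate is also less precise than the collected data allow.

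Leaving the method open adds a smaller problem. A follow-up score, a change score and a baseline-adjusted difference would each satisfy the wording, they differ in precision, and in an open trial the choice could be made after the data are seen.

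At stake are the width and credibility of the intervals on the patient-reported results.

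**Working it through.** **1. The plan's own figure.** Section 3.1 assumes means of 1,500 and 1,000 mL, ±500 mL (read as the SD), 90% power, two-sided alpha 0.05 and 10% loss.
- n per arm = 2 × (1.960 + 1.282)² × 500² / 500² = 21.01, rounded up to 22.
- 22 / 0.90 = 24.4, rounded up to 25 per arm, 50 in total.

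This reproduces the stated size. It concerns blood loss only; the documents give no SD, effect or power for the scores.

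**2. Chance imbalance at baseline.** In units of the score's SD, the standard deviation of the difference in baseline means is √(2/25) = 0.283.
- Probability that the arms differ by more than 0.25 SD: 2 × [1 − Φ(0.25/0.283)] = 0.38.
- Probability that they differ by more than 0.5 SD: 0.08.

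A fraction r of the imbalance is expected to carry into an unadjusted follow-up comparison, where r is the correlation between baseline and follow-up. With r = 0.5 and an imbalance of 0.28 SD, that is 0.14 SD.

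**3. Gain from adjustment.** r is not in the documents, so a range is assumed. Equal SDs at baseline and follow-up are also assumed. Variance of the arm difference relative to the follow-up score alone:
- baseline-adjusted: 1 − r², times 1 + 1/(N − 4) for estimating the slope; with N = 50 that factor is 1 + 1/46 = 1.022;
- simple change score: 2(1 − r).

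| r (assumed) | 1 − r² | with slope penalty | change score | 95% CI half-width, adjusted (SD) |
|---|---|---|---|---|
| 0.2 | 0.96 | 0.98 | 1.6 | 0.56 |
| 0.3 | 0.91 | 0.93 | 1.4 | 0.55 |
| 0.5 | 0.75 | 0.77 | 1.0 | 0.50 |
| 0.7 | 0.51 | 0.52 | 0.6 | 0.41 |

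The unadjusted half-width is 0.57 SD. Ignoring the slope penalty, adjustment at r = 0.3, 0.5 and 0.7 is worth 25/(1 − r²) = 27.5, 33.3 and 49.0 patients per arm.

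**4. With the planned 10% loss** (25 × 0.9 = 22.5 per arm), the unadjusted half-width is 0.60 SD. Adjusted, it is 0.58, 0.53 and 0.44 SD at r = 0.3, 0.5 and 0.7.

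The table covers the baseline covariate only. The smoking term is not included; randomization is stratified on it, so its main cost should be one residual degree of freedom.

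**The case against.** The strongest reply is that no inference is planned on these scores. They get descriptive statistics and are exploratory, and no test, margin, power or decision rests on them, so no promised precision is lost. The gain is also a generic formula with an assumed correlation; at r = 0.2 it is about 2% after the slope penalty. Both points stand. They limit how much this matters, but they do not make the unused baseline a better choice: the plan does intend a comparison between arms, and an adjusted difference with an interval can be reported under the exploratory label.

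Three stronger readings are tempting, and the documents do not support them.
- *The plan prescribes a comparison of raw follow-up scores.* It does not. It speaks of outcome scores compared between groups and excludes neither change from baseline nor adjustment. The method is unspecified.
- *The scores are meant to demonstrate that MONTAGE does no harm.* They stand under the safety headings in the Summary and section 4.1.2, but the explicit wording about no negative impact or interference belongs to the residual gap and new bone formation. Sections 1.4 and 6.1 list the scores as secondary.
- *Baseline SRS-22 will be missing.* Section 4.2.1.1 plainly requires it. The question mark in Appendix I is a conflict that could lead a site to omit it, not evidence that it is omitted.

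**Conclusion.** The point holds as a low-cost improvement to exploratory analyses. Baseline scores are collected, no baseline-adjusted estimate is specified, and at 25 per arm the comparison as written is open to chance imbalance (SD of the baseline mean difference 0.28 SD).

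The variance reduction from adjustment is about 9%, 25% or 49% at r = 0.3, 0.5 or 0.7, less about 2% for the slope, and negligible near 0.2. It depends on r, which the documents do not give, so no single figure can be defended.

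A reader might infer that the trial's main result is weakened. It is not: the blood-loss analysis and the sample size of 50 do not depend on these scores.

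**What to change.** 1. In section 6.3.2, state that for each score at Week 52 and at Week 104 the between-arm difference will be reported with a 95% confidence interval from a linear model on arm, baseline score and smoking stratum, labelled exploratory. Week 52 coincides with the CT scan and Week 104 is the last visit. Keep the other visits descriptive, and give the number analysed per arm.
2. Do not substitute an unadjusted change score, which is noisier than the follow-up score alone when r is below 0.5.
3. Reconcile Appendix I with section 4.2.1.1 on baseline SRS-22. Do this before further patients are operated on, because a missed pre-operative score cannot be recovered.
4. Reconcile NRS in the Summary with VAS elsewhere, so that pain at baseline and follow-up is the same measure.

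The cost is wording in the analysis section, the Summary and one table cell. It adds no patients, visits or assessments beyond those already required by section 4.2.1.1.

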1. INTRODUCTION

1.1 STATEMENT OF INTENT

The design, conduct and reporting of this trial shall be undertaken in compliance with the protocol, ICH/GCP and all appropriate regulatory requirements.

1.2 TITLE

A Prospective, Multicenter, Randomized, Controlled Clinical Investigation of MONTAGE in Adults with Spinal Deformity undergoing Pedicle Subtraction Osteotomy

1.3 BACKGROUND INFORMATION

PEDICLE SUBTRACTION OSTEOTOMY - ASSOCIATED BLOOD LOSS

Pedicle Subtraction osteotomy (PSO) is a surgical option for treating several spinal deformities. It has been utilized in alignment disorders of the fused spine, in the lumbar spine to treat large sagittal deformities and in patients with ankylosing spondylitis with thoracolumbar kyphotic deformity (1).

PSO is a procedure most commonly performed in the lumbar and thoracic spinal regions. PSO is often avoided in the distal lumbar spine because the risk of the neurologic injury is greater and fewer fixation points are available. It has been suggested that some of the ideal candidates for PSO are those patients with a substantial sagittal imbalance > 10 to 12 cm, with a sharp angular kyphosis and patients who have circumferential fusion along multiple segments. For most patients with ankylosing spondylitis, PSO could be the treatment of choice. The procedure involves surgical excision of a wedge of bone from the posterior spine (osteotomy). The two cut edges are then drawn together by a system of screws and rods designed to apply compression and thus reduce the unnatural forward curvature of the spine.

PSO typically results in substantial loss of blood (as much as 2L) with a significant portion of the loss likely occurring at the osteotomy surfaces post-surgically. Blood loss-associated morbidities can be direct, including hypotension, organ damage (particularly cardiac, pulmonary, renal) and coagulopathy. Excessive blood loss also may require allogeneic blood transfusion, which may further result in acute lung injury, hypersensitivity reactions, infections, and immune suppression. Another concern with regard to post-operative bleeding in spinal surgery is the risk of spinal epidural hematoma formation, which might lead to spinal cord or cauda equina compression. Therefore, the control of peri-operative blood loss is considered a critical issue by spine surgeons (2,3,5).

A variety of methods have been proposed for the reduction of blood loss during or immediately after spine surgery, including preoperative use of erythropoietin, autologous blood, cell salvage, intra-operative controlled hypotension, and the use of anti-fibrinolytic drugs (6). Bone hemostats have traditionally not been part of the standard of care to promote hemostasis probably because most available options (e.g., bone wax) are nonabsorbable and thus might interfere with fusion at the osteotomy site.

MONTAGE

MONTAGE is a settable (hardening) bioabsorbable polymer and hydroxyapatite/beta tricalcium phosphate based putty, used in the control of bleeding from bone during spine, orthopedic, craniomaxillofacial, thoracic and other surgical procedures.

It is easy to manipulate and typically results in immediate and complete cessation of bleeding at the bony defect. The putty hardens within minutes after application, remaining secure in place, without being dislodged or dissolved during the early stages of bone formation. In animal studies, the use of MONTAGE has not been shown to interfere with bone healing or fusion (7).

MONTAGE putty was implanted in rabbit diaphyseal femoral defects (N=12) and each defect was evaluated after 4 weeks by histopathology (8). The microscopic evaluation demonstrated no significant signs of inflammation or fibrosis, while there was indication that new bone formation occurred. MONTAGE is fully absorbed within approximately 1 year and is replaced with endogenous bone.

MONTAGE settable putty is FDA cleared as a bone hemostat in skeletal surgical procedures.

1.4 OBJECTIVES

The primary objective of this study is to evaluate the difference in postoperative bleeding between two study groups, FDA cleared MONTAGE and standard of care (no bone hemostat), and the extent to which any transfusion is needed and blood loss is measured through drop in hematocrit (HCT), as well as wound drain output, if utilized. As an exploratory evaluation of the primary endpoints a calculation will be made of blood loss for the first 7 days following surgical procedure as assessed by a multivariate combination of these measures of blood loss.

The secondary objective is the stability of the construct, as measured by whether the correction has maintained stability at 1-year and 2-years post surgery. Each incidence of instability will be categorized as belonging to one of the following groups: 1) hardware malplacement, 2) loosening or dislodgment, 3) nonunion or nonfusion with hardware fracture 4) nonunion or nonfusion without hardware fracture and 5) perihardware fracture.

Each osteotomy site will be assessed using X-rays and with computed tomography (CT) scans – performed at 12 months post surgery. Failure of fusion will be determined to be present if an area of bone apposition lucency greater than 2mm in thickness is present.

Secondary objectives will also include:

- The formation of new bone, as measured by CT scans at 1-year post surgery,
- Evaluation of Visual Analog Scale (VAS) back and leg pain, Oswestry Disability Index (ODIv2.1a), and SRS-22 scores, which will be recorded during the study and compared between the two groups.
- Evaluation of work status.
- Antifibrinolytics use and type will be recorded during the study and compared between the two groups

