4.2.3.6 Visit #7: Follow-up visit (Week 52)

Radiographs- standing ap and lateral scoli xrays will be completed and centrally read by independent evaluators.
VAS back and leg, ODIv2.1a and SRS-22 scores will be collected
Current pain medications/dosing will be collected.
Angular correction and gap will be measured.
A CT scan will be taken to evaluate screw loosening and other measures of bone healing.
Adverse Events will be recorded.

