4.2.3.7 Visit #8: Follow-up visit (Week 104)

Radiographs standing ap and lateral scoli xrays will be completed and centrally read by independent evaluators.
VAS back and leg, ODIv2.1a and SRS-22 scores will be collected
Current Pain medications/dosing will be collected.
Angular correction and gap will be measured.
Adverse Events will be recorded.

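### The plan does not say how a construct revised before 1 or 2 years counts, so a post-revision gap can enter the safety comparison as a good result

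*Combined protocol and SAP*

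**What the plan says.** **Stability.** Section 1.4 makes construct stability the secondary objective, "as measured by whether the correction has maintained stability at 1-year and 2-years post surgery". The next sentence adds that "Each incidence of instability will be categorized as belonging to one of the following groups", and lists five categories. Section 6.1 defines the same outcome differently and gives no time point: "The secondary outcome will be the stability of the construct, as measured by the gap between the repaired osteotomy edges". It then lists the same five categories and states: "These complications will be measured with imaging, including CT scans performed at 1-year".

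**Gap as a safety comparison.** The Summary (Safety Endpoints) and section 4.1.2 say that "any residual gap will be measured in millimeters and compared between the groups", using the 1-year CT and a two-sided t test. The stated purpose is to show that MONTAGE does not harm the result of the osteotomy.

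**Imaging.** Section 1.4 places the CT at one time point: "computed tomography (CT) scans – performed at 12 months post surgery". The Week 52 visit says: "A CT scan will be taken to evaluate screw loosening and other measures of bone healing". The Week 104 visit says: "Radiographs standing ap and lateral scoli xrays will be completed and centrally read by independent evaluators", with angle and gap measured. It lists no CT, and Appendix I shows none after Week 52.

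**Analysis set.** Section 6.3.1 defines the ITT population as all subjects who received study treatment. Section 6.3 mentions a Per Protocol analysis but does not define it.

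**Revision.** No section mentions revision or reoperation, or says how images taken after one are used.

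**The concern.** Take a patient whose rod breaks at month 8 with non-union and whose construct is then revised. At Week 52 the CT shows the re-compressed osteotomy and the new hardware. The gap may be small and the correction present. Nothing in the plan removes or flags that scan, so the value goes into the gap t test as a good result. Section 1.4 can also be read so that the patient is stable at 1 year, because the correction is there when it is looked at.

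The treatment of the failure has then turned a poor outcome into favourable data. The gap comparison is the plan's structural safety test, and section 1.3 itself notes that some bone hemostats might interfere with fusion. If failures were commoner with MONTAGE, this would hide the harm. Surgeons know the allocation, so the decision to revise could also differ by arm, and blinded reading of the images cannot correct for that.

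**Working it through.** **1. Number evaluable.** The documents give no figure for stability, so I take the number from the blood-loss calculation in section 3.1: difference 1,500 − 1,000 = 500 mL, SD 500 mL (reading the ± as an SD), 90% power, two-sided alpha 0.05, 10% loss.

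- n per arm = 2 × (1.960 + 1.282)² × (500/500)² = 21.0, just over 21, so 22.
- With 10% loss: 22/0.9 = 24.4, so 25 per arm and 50 in total. This reproduces the plan's figure.

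I use 22 evaluable per arm below. It is an assumption for stability, since the 10% loss was set for blood loss and not for 1-year or 2-year imaging.

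**2. Effect of one misclassified patient.** 1/22 = 0.045, or 4.5 percentage points of that arm's instability rate.

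**3. How the text treats the month-8 patient.**

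| Question | Answer in the plan |
|---|---|
| Is the patient in the analysis set? | Yes (6.3.1) |
| Is the Week 52 gap used in the t test? | Yes; no exception is made (Summary, 4.1.2) |
| Is the month-8 event recorded? | Yes, as an adverse event, and it fits category 3 (1.4, 5.1, 6.1) |
| Does the event make the patient unstable at 1 year or 2 years? | Not stated |

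**4. Illustration for the instability rate (all rates assumed).** Suppose true failure by 2 years is 10% with control and 30% with MONTAGE. Suppose a share r of failures in both arms is revised and then scored stable. Visible rate = true rate × (1 − r). Power is for an exact two-sided Fisher test with 22 per arm.

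| r | Visible rates | Difference | Power |
|---|---|---|---|
| 0 | 10% vs 30% | 20 points | 28% |
| 0.25 | 7.5% vs 22.5% | 15 points | 18% |
| 0.50 | 5% vs 15% | 10 points | 9% |
| 0.75 | 2.5% vs 7.5% | 5 points | 1% |

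At r = 0 the expected failures are 22 × 0.10 = 2.2 and 22 × 0.30 = 6.6. If the shares differ by arm, the distortion can be larger. With half of the MONTAGE failures masked and none of the control failures, the visible rates are 10% and 0.30 × 0.5 = 15%, a difference of 5 points.

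**5. Illustration for the gap (values assumed).** Let the gap be 1 mm if stable, 4 mm if failed and 1 mm after revision. Mean gap = 1 + 3 × failure rate × (1 − r).

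- r = 0: 1.3 mm vs 1.9 mm, difference 0.6 mm.
- r = 0.5: 1.15 mm vs 1.45 mm, difference 0.3 mm.

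These examples show direction and mechanism. They do not estimate what will happen in this trial.

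**The case against.** The strongest reply is that the plan does not ignore what happens between visits. Section 1.4 asks that every incidence of instability be categorised, and section 6.1 says the same of every repair complication. That wording leans towards cumulative counting, and the month-8 patient fits one of the listed categories. The tense in "as measured by whether the correction has maintained stability at 1-year and 2-years post surgery" can also be read as failing a patient who needed revision. Radiographs are taken at Weeks 2, 6, 12 and 24, with angle and gap measured from Week 6 in the visit text (from Week 12 in Appendix I). Adverse events are recorded to the final visit and compared by arm, and a revision needing hospital admission is an SAE under section 5.2. Images are read blind, and section 6.3.2 calls secondary analyses exploratory.

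Much of this stands. A reader might infer that stability is judged at two snapshots whatever happened in between, or that a failure seen on the 1-year CT is erased at 2 years. The documents say neither. They do not say that the later reading replaces the earlier one, and hardware assessment is not confined to CT.

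What remains is that categorising an event does not say whether it counts in the 1-year or 2-year status, and it does nothing for the gap t test. Two analysts could score the same patient in opposite ways. Exploratory status is also a weak defence for the gap, which the Summary and section 4.1.2 present as a safety comparison.

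**Conclusion.** The point holds as a gap in pre-specification. For the t test it has a definite consequence: as written, a post-revision gap enters as a good result. For the instability categories the text leans towards cumulative counting but does not settle it. The blood-loss endpoint and the sample size are unaffected.

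The size cannot be determined. The 4.5 points per patient rests on the assumed 22 evaluable per arm, and every failure, revision and gap value in the illustrations is assumed. It is possible in an open trial that revision decisions differ by arm, but nothing in the documents shows it.

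A reader might want to judge a shift in mean gap against the 2 mm in sections 1.4 and 6.1. That figure is a lucency thickness in a single patient. It is neither a limit for the gap nor a margin between arms, so the comparison has no meaning.

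**What to change.** 1. **Sections 1.4 and 6.1.** Define instability as cumulative: any of the five categories, or any revision of the PSO construct for one of them, by 1 year and by 2 years counts as failure. Use the scheduled imaging and the SAE records as sources.
2. **Same sections.** Report two separate summaries: 1-year status from CT plus radiographs, and 2-year status from radiographs plus events categorised earlier. They rest on different imaging, so the two rates should not be read as a trend. Counting an earlier non-union at 2 years even if it later unites is a choice of what to estimate, and the text should say so.
3. **Summary and section 4.1.2.** Compare the 1-year gap by a rank test, with patients revised for instability before that scan ranked worst. Keep the planned t test on observed gaps as a sensitivity analysis.

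Substituting the last gap measured before revision would be a poor alternative. For a month-8 failure the last scheduled image may be the Week 24 radiograph, taken before the rod broke, and it would mix radiograph and CT measurements in one test.

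**Cost.** Wording in the three numbered sections and the Summary, plus one extra analysis. The rule uses images and SAE records already planned, and the sample size does not change. The reported instability rate will be slightly less favourable.
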